9.2.2.3 Functional Assessment of Cancer Therapy Kidney Symptom Index – Disease-Related Symptoms

The FKSI-DRS is a patient-reported instrument that measures whether the participant has experienced any of the following 9 kidney cancer-related symptoms: lack of energy, fatigue, weight loss, pain, bone pain, shortness of breath, cough, fever, or blood in the urine [Cella, D., et al 2007]. Each item is scored by using the following 5 response categories: 0, not at all; 1, a little bit; 2, somewhat; 3, quite a bit; and 4, very much. Responses to all FKSI-DRS items are summed to generate a summary symptom score ranging from 0 to 36, with higher scores indicating improved (more favorable) symptom status. The FKSI-DRS is a reliable, valid, and responsive brief index of the most important symptoms associated with advanced kidney cancer [Cella, D., et al 2007].

If, at the time of first dose of study treatment, the translated version of the FKSI-DRS – one of the PRO measures – is not available for that language/country, and it cannot be completed by the participant at Cycle 1, Day 1, then the FKSI-DRS will not be required for this participant at any point of the study. The other study PRO measures must be completed as scheduled.

Note: For some sites, the translated FKSI-DRS might become available after study startup and should be administered to participants at their time of first dose of study treatment; for some sites, the FKSI-DRS translation might not be available for the entire duration of the study. Missing FKSI-DRS for such a reason will not be considered a protocol deviation.

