3.4.3 Patient Reported Outcome (PRO) Endpoints

3.4.3.1 Secondary

- Mean change from baseline in EORTC QLQ-C30 global health status/quality of life scores.
- Mean change from baseline in EORTC QLQ-C30 functional subscales: physical functioning.
- Mean change from baseline in FKSI-DRS score.

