3.4.3.2 Exploratory

Following are the PRO endpoints which are going to be used for exploratory analyses:

- Mean change from baseline in EORTC QLQ-C30 symptom subscales: nausea and vomiting symptom, diarrhea symptom.
- Mean change from baseline in EQ-5D-5L Health State Score using visual analogue scale (VAS).
- Proportions of deterioration / stability / improvement / stability + improvement in EORTC QLQ-C30 global health status / QoL, its functional (physical functioning) where
 - Improvement is defined as a 10 points or more increase in score (in the positive direction) from baseline at any time during the study and confirmed by a 10 points or more improvement at the next consecutive visit.
 - Stability is defined as, when the criteria for improvement are not met, a less than 10 points worsening in score from baseline at any time during the study and confirmed by a less than 10 points worsening at the next consecutive visit.
 - Stability + improvement is defined as an improvement or less than 10 points worsening in score from baseline at any time during the trial and confirmed by an improvement or less than 10 points worsening in score at the next consecutive visit.
 - Deterioration is defined as, when the criteria for improvement or stability are not met, a 10 points or greater worsening from baseline at any time during the study.

- Proportions of deterioration / stability / improvement / stability + improvement in FKSI-DRS score where
 - Improvement is defined as a 3-points or more increase in score (in the positive direction) from baseline at any time during the study and confirmed by a 3-points or more improvement at the next consecutive visit.
 - Stability is defined as, when the criteria for improvement are not met, a less than 3 points worsening in score from baseline at any time during the study and confirmed by a less than 3 points worsening at the next consecutive visit.
 - Stability + improvement is defined as an improvement or less than 3 points worsening in score from baseline at any time during the trial and confirmed by an improvement or less than 3 points worsening in score at the next consecutive visit.
 - Deterioration is defined as, when the criteria for improvement or stability are not met, a 3 points or greater worsening from baseline at any time during the study.

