3.6.4.1 PRO compliance summary

Completion and compliance of EORTC QLQ-C30, FKSI-DRS and EQ-5D by visit and by treatment will be described. Numbers and percentages of complete and missing data at each visit will be summarized. An instrument is considered complete if at least one valid score is available according to the missing item rules outlined in the scoring manual for the instrument.

Completion rate of treated participants (CR-T) at a specific time point is defined as the number of treated participants who complete at least one item over the number of treated participants in the PRO analysis population.

$$CR-T = \frac{\text{Number of treated participants who complete at least one item}}{\text{Number of treated participants in the PRO analysis population}}$$

The completion rate is expected to shrink in the later visit during study period due to the participants who discontinued early. Therefore, another measurement, compliance rate of eligible participants (CR-E) will also be employed as the support for completion rate. CR-E is defined as the number of treated participants who complete at least one item over number of eligible participants who are expected to complete the PRO assessment, not including the participants missing by design such as death, discontinuation, translation not available.

$$CR-E = \frac{\text{Number of treated participants who complete at least one item}}{\text{Number of eligible participants who are expected to complete}}$$

The reasons of non-completion and non-compliance will be provided in supplementary table:

- Completed as scheduled
- Not completed as scheduled
- Off-study: not scheduled to be completed.

In addition, reasons for non-completion as scheduled of these measures will be collected using “miss_mode” forms filled by site personnel and will be summarized in table format. The

schedule (study visits and estimated study times) and mapping of study visit to analysis visit for PRO data collection is provided in [Table 4](#).

Table 4 PRO Data Collection Schedule and Mapping of Study visit to Analysis Visit

Study Week	Week 0 (Baseline)	Week 12	Week 24 to Week 36 (Every 12 weeks)	Week 48	Week 52	Week 104 to Week 120 (Every 16 weeks)
Study Day	1	85	Week number *7+1	337	365	Week number *7+1
Day Range	<=1	[2, 126]	[Week number*7-41, week number*7+42]	[295, 351]	[352, 546]	[Week number*7-181, week number*7+182]

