3.6.4.2 Mean change from baseline

The time point for the mean change from baseline is defined as the latest time point at which CR-T ≥ 60% and CR-E ≥ 80% and week 52 was selected based on blinded data review prior to the database lock for any PRO analysis.

To assess the treatment effects on the PRO score change from baseline in the global health status/QoL and its physical functioning, nausea and vomiting symptom, diarrhea symptom, FKSI-DRS, EQ-5D-5L VAS outcome a constrained longitudinal data analysis (cLDA) model proposed by Liang and Zeger [4] will be applied, with the PRO score as the response variable, and treatment by time interaction and stratification factors used for randomization (See Section 7.3.1) as covariates. The treatment difference in terms of least square (LS) mean change from baseline will be estimated from this model together with 95% CI. Model-based LS mean with 95% CI will be provided by treatment group for PRO scores at baseline and post-baseline time point.

The cLDA model assumes a common mean across treatment groups at baseline and a different mean for each treatment at each of the post-baseline time points. In this model, the response vector consists of baseline and the values observed at each post-baseline time point. Time is treated as a categorical variable so that no restriction is imposed on the trajectory of the means over time. The cLDA model is specified as follows:

$$E(Y_{ijt}) = \gamma_0 + \gamma_{jt}I(t > 0) + \beta X_i, j = 1,2; t = 0,1,2,3, \dots k$$

where Y_{ijt} is the PRO score for participant i , with treatment assignment j at visit t ; γ_0 is the baseline mean for all treatment groups, γ_{jt} is the mean change from baseline for treatment group j at time t ; X_i is the stratification factor (binary) vector for this participant, and β is the coefficient vector for stratification factors. An unstructured covariance matrix will be used to model the correlation among repeated measurements. If the unstructured covariance model fails to converge with the default algorithm, then Fisher scoring algorithm or other appropriate methods can be used to provide initial values of the covariance parameters. In the rare event that none of the above methods yield convergence, a structured covariance such as Toeplitz

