can be used to model the correlation among repeated measurements. In this case, the asymptotically unbiased sandwich variance estimator will be used. The cLDA model implicitly treats missing data as missing at random (MAR).

Line plots for the empirical mean change from baseline in EORTC QLQ-C30 global health status/QoL, its physical functioning and FKSI-DRS will be provided across time points till Week 52 as a supportive analysis.

In addition, the model-based LS mean change from baseline to the specified post-baseline time point together with 95% CI will be plotted in bar charts for EORTC QLQ-C30 global health status/QoL and its each functioning scale, symptom scale and FKSI-DRS score.

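### The written FKSI-DRS scoring rule makes higher scores worse, while the protocol and sSAP read higher scores as better; no item reversal is stated

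*Combined protocol and SAP*

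**What the plan says.** Protocol section 9.2.2.3 describes the FKSI-DRS as nine kidney cancer symptoms, all of them adverse (for example pain, fever and blood in the urine). The response codes are "0, not at all; 1, a little bit; 2, somewhat; 3, quite a bit; and 4, very much". The next sentence gives the summary score: "Responses to all FKSI-DRS items are summed to generate a summary symptom score ranging from 0 to 36, with higher scores indicating improved" symptom status. Section 5.4.1.4 repeats the sum, the range and the direction, but gives no item codes.

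The sSAP uses the score in three places:

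- **Secondary PRO endpoint (3.4.3.1):** "Mean change from baseline in FKSI-DRS score".
- **Analysis (3.6.4.2):** the model sentence covers "FKSI-DRS, EQ-5D-5L VAS outcome a constrained longitudinal data analysis (cLDA) model", and "The treatment difference in terms of least square (LS) mean change from baseline will be estimated from this model together with 95% CI". There is also a display: "Line plots for the empirical mean change from baseline in EORTC QLQ-C30 global health status/QoL, its physical functioning and FKSI-DRS will be provided".
- **Exploratory classes for FKSI-DRS (3.4.3.2):** "Improvement is defined as a 3-points or more increase in score (in the positive direction) from baseline", confirmed at the next visit. Stability and deterioration use the same 3-point threshold.

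A scoring manual is mentioned once, in sSAP 3.6.4.1, where a questionnaire counts as complete if a valid score is available "according to the missing item rules outlined in the scoring manual for the instrument". That reference concerns missing items, not item direction.

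**The concern.** Section 9.2.2.3 gives the item content, the numeric codes, the operation, the range and the direction, so it reads as a complete scoring rule. The codes and the operation point one way and the stated direction points the other. The range does not help, because 0 to 36 is the range whether or not the items are reversed.

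A programmer or outside reader working from these two documents has to add a step that neither contains. If the step were left out, the direction of a listed secondary endpoint would be reported backwards, and worsening symptoms could be counted as improvement. The stakes stop there: sSAP 3.6.4 plans no formal hypothesis test and no multiplicity adjustment for PROs, and DFS, OS, alpha and power do not depend on this score.

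**Working it through.** **Inputs.** Nine items, codes 0 to 4, plain sum, stated range 0 to 36 with higher better (section 9.2.2.3); 3-point threshold with an increase meaning improvement (sSAP 3.4.3.2); cLDA model (sSAP 3.6.4.2).

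**1. Reproduce the range.** The minimum is 9 × 0 = 0 and the maximum is 9 × 4 = 36. The stated range is correct.

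**2. Check the direction.** Let x be an item response.

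| State | Literal score, Σx | Reversed score, Σ(4 − x) |
|---|---|---|
| No symptoms (all 0) | 0 | 36 |
| All symptoms at the top category (all 4) | 36 | 0 |

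Under the literal rule higher is worse. The stated direction is reproduced only by the reversed score. Since Σ(4 − x) = 36 − Σx, the two scores agree only when the sum is 18.

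**3. Effect on the secondary endpoint.** Let Y be the intended (reversed) score and Y′ = 36 − Y the literal one. The sSAP model is E(Y) = γ₀ + γ_jt·I(t > 0) + βX. Substituting,

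E(Y′) = (36 − γ₀) − γ_jt·I(t > 0) − βX.

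- The baseline mean becomes 36 − γ₀.
- Every mean change γ_jt becomes −γ_jt.
- The covariance matrix is unchanged, because Var(36 − Y) = Var(Y).
- A between-arm difference d with 95% CI (L, U) becomes −d with CI (−U, −L).
- The standard error is unchanged. The test statistic changes sign only, so a two-sided p value is the same. A one-sided p value would become 1 − p; the sSAP does not say which form the nominal PRO p values take.

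**4. Effect on the exploratory classes.** Take a participant with every item at 1 at baseline: literal sum 9, reversed score 36 − 9 = 27. Suppose the change below is seen at two consecutive visits.

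| Change | Literal score | Reversed score |
|---|---|---|
| Three items each one category worse | 9 → 12, +3: meets the written improvement rule | 27 → 24, −3: a 3-point worsening |
| Three items each one category better | 9 → 6, −3: a 3-point fall | 27 → 30, +3: meets the improvement rule |

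If every change from baseline is smaller than 3 points in either direction, the class is the same under both scorings. The documents contain no PRO data, so no misclassification rate can be given.

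**5. Look for the missing step.** Section 5.4.1.4 gives no codes and no reversal. In sSAP 3.4.3.2 the positive-direction wording confirms the intent but supplies no operation. sSAP 3.6.4.1 refers to the manual for missing items only. No reversal of FKSI-DRS items was found in either document.

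**The case against.** The strongest reply is that the intent is never in doubt. Sections 9.2.2.3 and 5.4.1.4 and sSAP 3.4.3.2 all say that higher is better, so anyone who sums unreversed codes breaches an explicit statement. On this reading the plan omits a clause and does not contain two rival rules. Section 9.2.2 also need not be a full algorithm: section 9.2.2.2 gives the EORTC QLQ-C30 only as 1–4 and 1–7 responses, yet sSAP 3.4.3.2 applies 10-point thresholds to its scales, so the conversion must lie elsewhere. A scoring manual is plainly in use and may prescribe the reversal.

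Much of this stands. The intended direction is clear, the manual may settle the matter, and the documents do not show that any data would be mis-scored. The analogy is incomplete, however. The QLQ-C30 text leaves a step out, whereas the FKSI-DRS text gives codes and an operation that contradict its own direction.

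A second reply is that a reversal error would be noticed, because sSAP 3.6.4.2 calls for model-based mean scores at baseline and afterwards. Participants enter tumor free with ECOG PS 0 or 1. If their symptom burden is low, literal scoring would put the baseline mean near 0, the supposedly worst end. That is a real safeguard, but it rests on an assumption about symptom burden that the documents cannot confirm, and on someone looking. An unchanged two-sided p value would give no warning.

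**Conclusion.** The point holds: the scoring rule in section 9.2.2.3 is wrong as written. Its codes and plain sum run opposite to the direction stated there and used in the sSAP.

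The size is conditional on literal use of the sum. In that case the signs of all FKSI-DRS mean changes and between-arm differences reverse with unchanged magnitude and standard error, and exploratory classes can be wrong for participants whose score moves by 3 points or more. If the analysis program already reverses the items, no result changes and only the text is at fault.

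Severity is minor. The endpoint is secondary but not formally tested, and the confirmatory analyses are unaffected. Confidence in the contradiction is high, because it follows from the text and simple arithmetic. Whether the manual or program contains the reversal cannot be seen from these documents.

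**What to change.** First check the instrument's scoring manual and the analysis program. Once reversal is confirmed, correct section 9.2.2.3 and add to sSAP 3.4.3 a sentence such as: *Each item is reverse-scored (4 minus response) before summing, so that 0 is the worst and 36 the best symptom status.*

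Keep the 3-point thresholds, which then agree with the stated direction. Section 5.4.1.4 needs no edit, because it gives the direction without item codes.

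The cost is one sentence in each of two sections and one check of the manual and program. No collected data change.

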9.3 Adverse Events, Serious Adverse Events and Other Reportable Safety Events

The definitions of an adverse event (AE) or serious adverse event (SAE), as well as the method of recording, evaluating, and assessing causality of AE and SAE and the procedures for completing and transmitting AE, SAE and other reportable safety event reports can be found in Appendix 4.

Progression of the cancer under study is not considered an adverse event as described in Section 9.3.5 – Disease-Related Events and/or Disease-Related Outcomes Not Qualifying as AEs or SAEs, and Appendix 4.

AE, SAEs, and other reportable safety events will be reported by the participant (or, when appropriate, by a caregiver, surrogate, or the participant's legally authorized representative).

The investigator, who is a qualified physician, and any designees are responsible for detecting, assessing, documenting, and reporting events that meet the definition of an AE or SAE as well as other reportable safety events. Investigators remain responsible for following up AE, SAEs and other reportable safety events for outcome according to Section 9.3.3.

9.3.1 Time Period and Frequency for Collecting AE, SAE and Other Reportable Safety Event Information

All AEs, SAEs and other reportable safety events that occur after the consent form is signed but before treatment allocation/randomization must be reported by the investigator if the participant is receiving placebo run-in or other run-in treatment, if the event cause the participant to be excluded from the trial, or is the result of a protocol-specified intervention, including but not limited to washout or discontinuation of usual therapy, diet, or a procedure.

- All AEs from the time of treatment allocation/randomization through 30 days following cessation of study treatment must be reported by the investigator.
- All AEs meeting serious criteria, from the time of treatment allocation/randomization through 90 days following cessation of study treatment, or 30 days following cessation of study treatment if the participant initiates new anticancer therapy, whichever is earlier must be reported by the investigator.
- All pregnancies and exposure during breastfeeding, from the time of treatment allocation/randomization through 120 days following cessation of study treatment, or 30 days following cessation of study treatment if the participant initiates new anticancer therapy must be reported by the investigator.
- Additionally, any SAE brought to the attention of an investigator at any time outside of the time period specified above must be reported immediately to the Sponsor if the event is considered to be drug-related.

Investigators are not obligated to actively seek AE or SAE in former study participants. However, if the investigator learns of any SAE, including a death, at any time after a participant has been discharged from the study, and he/she considers the event to be reasonably related to the study treatment or study participation, the investigator must promptly notify the sponsor.

All initial and follow-up AEs, SAEs and other reportable safety events will be recorded and reported to the sponsor or designee within the timeframes as indicated in [Table 8](#).

Table 8 Reporting Time Periods and Timeframes for Adverse Events and Other Reportable Safety Events

Type of Event	Reporting Time Period: Consent to Randomization/ Allocation	Reporting Time Period: Randomization/ Allocation through Protocol-Specified Follow-up Period	Reporting Time Period: After the Protocol Specified Follow-up Period	Timeframe to Report Event and Follow-up Information to SPONSOR:
Serious Adverse Event (SAE) including Cancer and Overdose	Report if: - due to protocol-specified intervention - causes exclusion - participant is receiving placebo run-in or other run-in treatment	Report all	Report if: - drug/vaccine related. (Follow ongoing to outcome)	Within 24 hours of learning of event
Non-Serious Adverse Event (NSAE)	Report if: - due to protocol-specified intervention - causes exclusion - participant is receiving placebo run-in or other run-in treatment	Report all	Not required	Per data entry guidelines
Event of Clinical Interest (require regulatory reporting)	Report if: - due to intervention - causes exclusion	Report - Potential DILI - Require regulatory reporting	Not required	Within 24 hours of learning of event
Event of Clinical Interest (Do not require regulatory reporting)	Report if: - due to intervention - causes exclusion	Report - non-DILI ECIs and those not requiring regulatory reporting	Not required	Within 5 days of learning of event
Pregnancy/Lactation Exposure	Report if: - due to intervention - causes exclusion	Report all	Previously reported – Follow to completion/termination; report outcome	Within 24 hours of learning of event

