AE Monitoring	X	X	X	X	X	X	X	X	X	X	X	X	X	X	Record all AEs and ECIs occurring within 30 days after the last dose of study treatment and SAEs for 90 days after the end of treatment or 30 days after end of treatment if the participant initiates new anticancer treatment (whichever is earlier). Participants with an AE of Grade >1 will be followed until the resolution of the AE to Grade 0-1 or until the beginning of a new anticancer treatment, whichever occurs first. Report treatment-related SAEs regardless of when they occur.
ECOG PS	X	X	X	X	X	X	X	X	X	X	X	X	X ^f		

Trial Period:	Screening	Treatment									End of Treatment	Posttreatment Period			Notes
Treatment Cycle/Visit		1	2	3	4	5	6	7	8 ^a	9 ^a	Discon	Safety	Efficacy Follow-up	Survival Follow-up ^b	
Scheduling Window (Days)	-42 to -1 ^c		±3	±3	±3	±3	±3	±3	Repeat ±3	Repeat ±3	At time of discon	30 days post last dose (+7 days)	Every 12, 16, or 24 weeks (±7 days)	Every 12 weeks (±7 days)	Cycles 8 and 9 will be repeated up to 4 times, for a total of 17 doses of study treatment.
Future Biomedical Research/Biomarkers															
Tissue Collection for Biomarker Studies	X ^g														Submit tumor tissue from nephrectomy and/or for M1 NED participants, tumor tissue from resected metastatic lesion(s), as indicated in Section 9.7.1. Adequacy of the sample for biomarker analysis will be evaluated by a central laboratory.
Blood for Genetic Analysis ^h		X													Collect predose.
Blood for RNA Analyses		X	X			X					X		X		Collect predose at Cycles 1, 2, and 5, at treatment discontinuation (due to any reason), and during Follow-up at disease recurrence.
Blood for TCR		X	X			X					X		X		Collect predose at Cycles 1, 2, and 5, at treatment discontinuation (due to any reason), and during Follow-up at disease recurrence.

Trial Period:	Screening	Treatment									End of Treatment	Posttreatment Period			Notes
Treatment Cycle/Visit		1	2	3	4	5	6	7	8 ^a	9 ^a	Discon	Safety	Efficacy Follow-up	Survival Follow-up ^b	
Scheduling Window (Days)	-42 to -1 ^c		± 3	± 3	± 3	± 3	± 3	± 3	Repeat ±3	Repeat ±3	At time of discon	30 days post last dose (+7 days)	Every 12, 16, or 24 weeks (±7 days)	Every 12 weeks (±7 days)	Cycles 8 and 9 will be repeated up to 4 times, for a total of 17 doses of study treatment.
Blood for Plasma Biomarker Analyses		X	X			X					X		X		Collect predose at Cycles 1, 2, and 5, at treatment discontinuation (due to any reason), and during Follow-up at disease recurrence.

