Participants may receive study treatment for up to 17 cycles (approximately 1 year) or until confirmation of disease recurrence or meeting the criteria for discontinuation of study treatment as outlined in Section 8.

Participants who discontinue from treatment without documented disease recurrence should have imaging performed at the time of discontinuation if the last assessment was more than 28 days prior AND should continue with posttreatment Follow-up procedures until disease recurrence, pregnancy, the start of new anticancer treatment, death, withdrawal of consent, or study conclusion (whichever occurs first).

The End of Treatment Visit should occur at the time study treatment is discontinued for any reason (see Section 9.10.4.).

Posttreatment Follow-up Period

After the end of treatment, each participant will undergo a Safety Follow-up Visit at least 30 days (+ 7 days) after the last dose of study treatment or before the initiation of a new anticancer treatment, whichever comes first. Participants will be followed for 30 days after the last dose of study treatment for AE/ECI monitoring (SAEs will be collected up to 90 days

after the last dose of study treatment or for 30 days following cessation of treatment if the participant initiates new anticancer therapy, whichever comes first).

All participants who complete 17 cycles or discontinue from treatment for a reason other than disease recurrence will undergo radiographic imaging follow-up (Q12W during year 1, Q16W during years 2 to 4, then Q24W in years 5 and beyond) for assessment of DFS. Imaging during follow-up should continue to be scheduled from the date of randomization. QoL questionnaires will continue to be collected once per year during the follow-up period. Survival Follow-up for survival status and the initiation of subsequent anticancer treatment will be assessed Q12W.

[figure not shown]
Three efficacy interim analyses may be conducted; see Section 10.7 for details.

Specific procedures to be performed during the trial, as well as their prescribed times and associated visit windows, are outlined in the Trial SoA - Section 2. Details of each procedure are provided in Section 9 – Study Assessments and Procedures.

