7.2 Dose Modification (Escalation/Titration/Other)

7.2.1 Dose Modification and Toxicity Management Guidelines for Pembrolizumab

Dose Modification and Toxicity Management for Immune-related Adverse Events Associated With Pembrolizumab

AEs associated with pembrolizumab exposure may represent an immunologic etiology. These irAEs may occur shortly after the first dose or several months after the last dose of pembrolizumab treatment and may affect more than one body system simultaneously. Therefore, early recognition and initiation of treatment is critical to reduce complications. Based on existing clinical trial data, most irAEs were reversible and could be managed with interruptions of pembrolizumab, administration of corticosteroids, and/or other supportive care. For suspected irAEs, ensure adequate evaluation to confirm etiology or exclude other causes. Additional procedures or tests such as bronchoscopy, endoscopy, or skin biopsy may be included as part of the evaluation. Based on the severity of irAEs, withhold or permanently discontinue pembrolizumab and administer corticosteroids. Dose modification and toxicity management guidelines for irAEs associated with pembrolizumab are provided in [Table 5](#).

Table 5 Dose Modification and Toxicity Management Guidelines for Immune-related Adverse Events Associated With Pembrolizumab

General instructions:				

 1. Corticosteroid taper should be initiated upon AE improving to Grade 1 or less and continue to taper over at least 4 weeks. 2. For situations where pembrolizumab has been withheld, pembrolizumab can be resumed after AE has been reduced to Grade 1 or 0 and corticosteroid has been tapered. Pembrolizumab should be permanently discontinued if AE does not resolve within 12 weeks of last dose or corticosteroids cannot be reduced to ≤ 10 mg prednisone or equivalent per day within 12 weeks. 3. For severe and life-threatening irAEs, IV corticosteroids should be initiated first, followed by oral steroids. Other immunosuppressive treatment should be initiated if irAEs cannot be controlled by corticosteroids. 				
Immune-related AEs	Toxicity grade or conditions (CTCAEv4.0)	Action taken to pembrolizumab	irAE management with corticosteroid and/or other therapies	Monitor and follow-up

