9.1.5.2.1 Poststudy Anticancer Therapy

If a participant initiates a new anticancer therapy while receiving study treatment, study treatment must be discontinued and the participant will move into the Survival Follow-up phase. If a participant initiates a new anticancer therapy within 30 days after the last dose of study treatment, the End of Treatment Visit and the 30-day Safety Follow-up Visit must occur before the first dose of the new therapy. All new anticancer therapy initiated after the study start must be recorded in the poststudy anticancer therapy eCRF.

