9.11 Medical Resource Utilization and Health Economics

All-cause hospitalizations and emergency department visits must be reported in the eCRF, from the time of treatment allocation/randomization through 90 days following cessation of study treatment, or 30 days following cessation of study treatment, if the participant initiates new anticancer therapy, whichever is earlier.

10. Statistical Analysis Plan

This section outlines the statistical analysis strategy and procedures for the study. If, after the study has begun, changes are made to primary and/or key secondary hypotheses, or the statistical methods related to those hypotheses, then the protocol will be amended (consistent with ICH Guideline E9). Changes to exploratory or other nonconfirmatory analyses made after the protocol has been finalized, but prior to the conduct of any analysis, will be documented in a sSAP and referenced in the Clinical Study Report for the study. Separate analysis plans may be developed for PK/modeling analysis, biomarker analysis, and genetic data analysis. Post hoc exploratory analyses will be clearly identified in the Clinical Study Report. The PRO analysis plan will be included in the sSAP.

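### The shortened SAE window is counted from the end of study treatment, not from the start of new anticancer therapy, so some SAEs not judged drug-related before that therapy need not be reported

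*Combined protocol and SAP*

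**What the plan says.** Section 9.3.1 of the protocol sets the SAE window as "90 days following cessation of study treatment, or 30 days following cessation of study treatment if the participant initiates new anticancer therapy, whichever is earlier". The AE Monitoring note in the Schedule of Activities repeats the shortened limit: "30 days after end of treatment if the participant initiates new anticancer treatment (whichever is earlier". So does Section 5.1, under posttreatment follow-up: "for 30 days following cessation of treatment if the participant initiates new anticancer therapy, whichever comes first". Section 9.11 uses the same construction for hospitalizations and emergency department visits: "or 30 days following cessation of study treatment, if the participant initiates new anticancer therapy, whichever is earlier".

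Two provisions limit the effect. An SAE outside the window "must be reported immediately to the Sponsor if the event is considered to be drug-related" (Section 9.3.1), and the Schedule of Activities adds "Report treatment-related SAEs regardless of when they occur".

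Section 9.1.5.2.1 covers only early starts. If new therapy begins within 30 days of the last dose, "the End of Treatment Visit and the 30-day Safety Follow-up Visit must occur before the first dose of the new therapy". It has no matching rule for therapy that begins on days 31 to 90.

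**The concern.** An exception of this kind should keep events caused by the next therapy out of the study's SAE data. A cut at day 30 does not do that when the next therapy begins later. It also leaves out time in which the participant had received nothing but study treatment. Because 30 is always less than 90, the instruction to take the earlier limit does no work. It would matter only if one of the two limits were a variable date, such as the start of therapy.

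For the affected days, capture of an SAE depends on the investigator's causality call. Section 7.2.1 shows why that is uncomfortable for this drug: "These irAEs may occur shortly after the first dose or several months after the last dose of pembrolizumab treatment". All-cause collection exists so that the comparison does not rest on that call.

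Recurrence ends study treatment (Section 8.1) and commonly leads to new therapy. If the treatment works as designed, the window would be cut more often on placebo.

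**Working it through.** **The rule as written.** The plan states no figure for this point, so there is none to reproduce. Let *s* be the day after cessation on which new therapy starts.

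- Window end = min(90, 30) = 30 for any *s*.
- Pre-therapy days outside the window = max(0, min(*s*, 90) − 30).

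| *s* | Days outside |
|---|---|
| 30 or less | 0 |
| 45 | 15 |
| 60 | 30 |
| 75 | 45 |
| 90 or later | 60 |

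These are maxima. An SAE the site learns of before therapy starts is reportable at that time, because the 90-day limit still applies.

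**When the site would learn of an event.** Participants who stop for recurrence do not enter efficacy follow-up. Their first survival contact is 12 weeks after the discontinuation visit or the Safety Follow-up Visit, whichever is later (Section 9.10.4.3). If the safety visit falls on days 30 to 37, that contact falls on about days 30 + 84 = 114 to 37 + 84 = 121. An SAE on day 45 may therefore first be heard of after therapy has begun.

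**How many participants could be affected.** Inputs from Section 10.9 and Appendix 7: 990 participants, 1:1, so 495 per arm; HR 0.67; cure rate 0.3; S(t) = exp(−θ(1 − exp(−λt))), with θ = −ln 0.3 = 1.204. As a check on the HR, 332 events give 95.4% power in a fixed design and 95.1% with the two stated DFS bounds. The plan states about 95%.

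The 45-month control median is described in two ways:

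- Reading A, whole control arm (Section 10.1): S(45) = 0.5, so λ = −ln(1 − ln 2/θ)/45 = 0.0191 per month.
- Reading B, those not cured (Section 10.9): S(45) = 0.3 + 0.7 × 0.5 = 0.65, so λ = −ln(1 + ln 0.65/θ)/45 = 0.0098 per month.

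DFS events by 12 months are 1 − S(12) on placebo and 1 − S(12)^0.67 on pembrolizumab:

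| Reading | Placebo | Pembrolizumab | Ratio |
|---|---|---|---|
| A | 21.8% (108) | 15.2% (75) | 1.44 |
| B | 12.6% (62) | 8.6% (43) | 1.46 |

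DFS events include deaths, so these counts are upper bounds for recurrences.

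**Effect on SAE counts.** The documents do not give the next three inputs, so they are assumed: 25-75% of these participants affected, 1-5% SAE risk per 30 days in both arms, and 15-60 days lost. SAEs left out per arm = participants × share × risk × days/30.

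- Highest (reading A): placebo 108 × 0.75 × 0.05 × 2 = 8.1; pembrolizumab 75 × 0.75 × 0.05 × 2 = 5.6. Shift in the difference: (0.218 − 0.152) × 0.075 = 0.5 percentage points.
- Middle (reading A; 50%, 3%, 30 days): about 1.6 vs 1.1; shift 0.1 points.
- Lowest (reading B): about 0.08 vs 0.05; shift 0.005 points.

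Counting DFS events to month 15 instead of month 12 raises the highest case to about 0.6 points. All these figures treat every SAE on the affected days as lost, which overstates the loss.

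**The case against.** The strongest reply is that reporting is prospective. SAEs are due within 24 hours of the site learning of them, and no passage says an SAE already reported on day 45 is removed when therapy starts on day 75. That stands, and it confines the gap to events learned of after therapy begins. It does not close the gap, because the next scheduled contact can be months away.

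Much of the remaining content is covered elsewhere. Drug-related SAEs have no time limit, progression is not reportable in any window, and deaths are captured through survival follow-up. What is left is mainly non-fatal SAEs judged unrelated.

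A reader might infer three stronger points that the documents do not support:

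- *SAEs in general go uncollected after day 30.* The drug-related exception rules this out.
- *A planned between-arm interval for all-cause SAEs is compromised.* Table 12 and sSAP Table 3 place the any-serious-AE summary in Tier 3, which is descriptive. Between-arm CIs apply only to specific SAEs with incidence of at least 5%, and the plan calls those CIs descriptive too.
- *The rule flatters pembrolizumab.* With equal SAE rates in the two arms, the larger undercount is on placebo, so pembrolizumab would look slightly worse.

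The imbalance itself is an inference, since the documents give no timing of new therapy by arm. The sSAP expects longer follow-up on pembrolizumab and allows exposure-adjusted AE analyses, but only as an option. Section 10.9 also suggests that randomization is complete, so new wording alone would help few participants.

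**Conclusion.** The drafting problem is real and appears in all four places. Required reporting of SAEs not judged drug-related ends at day 30 once new therapy is initiated, whenever it starts. SAEs from day 31 to that start, at most day 90, are therefore not required if the site learns of them only after therapy begins.

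The consequence is small: at most about 0.5 percentage points on the between-arm SAE difference for DFS events by 12 months, and probably much less. That size rests on assumed SAE rates, days lost and share of participants affected. The direction, an undercount on placebo, rests on HR 0.67 and equal SAE rates in the two arms. It would reverse only if unreported SAEs per affected participant were more than about 1.4 times as frequent on pembrolizumab. No efficacy conclusion or formal test is touched. This is a cheap improvement to safety data collection.

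**What to change.** In Section 9.3.1, the Schedule of Activities (AE Monitoring), Section 5.1 and Section 9.11, end the window at the earlier of 90 days after cessation of study treatment or the start of new anticancer therapy, but in no case before 30 days after cessation. Use the same cut-off in the SAE tables, and state that SAEs already reported before therapy start are kept. The start date is available, because Section 9.1.5.2.1 already requires new anticancer therapy to be recorded in its own eCRF. The pregnancy item in 9.3.1 has a similar 120/30-day form and should be checked at the same time.

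For participants already affected, query SAEs from day 31 to therapy start, at most day 90. The cost is a wording change, a small data-management query and slightly higher SAE counts.
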